6.2 Management of Toxicities Attributable to Pembrolizumab

AEs associated with pembrolizumab exposure may represent an immunologic etiology. These immune-related AEs (irAEs) may occur shortly after the first dose or several months after the last dose of pembrolizumab treatment and may affect more than one body system simultaneously. Therefore, early recognition and initiation of treatment is critical to reduce complications. Based on existing clinical study data, most irAEs were reversible and could be managed with interruptions of pembrolizumab, administration of corticosteroids and/or other supportive care. For suspected irAEs, ensure adequate evaluation to confirm etiology or exclude other causes. Additional procedures or tests such as bronchoscopy, endoscopy, skin biopsy may be included as part of the evaluation.

Based on the severity of irAEs, withhold or permanently discontinue pembrolizumab and administer corticosteroids. Dose modification and toxicity management guidelines for irAEs associated with pembrolizumab are provided in Table 4.

Key dose modification management steps to highlight include:

- Permanently discontinue pembrolizumab for recurrent grade 2 pneumonitis.
- Permanently discontinue pembrolizumab for any instance of myocarditis, regardless of grade.

Subjects receiving corticosteroids for treatment of drug-related adverse events must be at \leq 10 mg/day prednisone or equivalent prior to re-initiation of pembrolizumab.

Table 4. Dose modification and toxicity management guidelines for immune-related AEs associated with pembrolizumab

General instructions:				
irAEs	Toxicity grade (CTCAE V5.0)	Action with pembrolizumab	Corticosteroid and/or other therapies	Monitoring and follow-up
Pneumonitis	Grade 2	Withhold	
• Administer corticosteroids (initial dose of 1 - 2 mg/kg prednisone or equivalent) followed by taper	
• Monitor participants for signs and symptoms of pneumonitis• Evaluate participants with suspected pneumonitis with radiographic imaging and initiate corticosteroid treatment
	Grade 3 or 4, or recurrent Grade 2	Permanently discontinue		

			
 • Add prophylactic antibiotics for opportunistic infections 	
Diarrhea / Colitis	Grade 2 or 3	Withhold	
 • Administer corticosteroids (initial dose of 1 - 2 mg/kg prednisone or equivalent) followed by taper 	
 • Monitor participants for signs and symptoms of enterocolitis (ie, diarrhea, abdominal pain, blood or mucus in stool with or without fever) and of bowel perforation (ie, peritoneal signs and ileus)
	Grade 4 or recurrent Grade 3	Permanently discontinue		
 • Participants with \geqGrade 2 diarrhea suspecting colitis should consider GI consultation and performing endoscopy to rule out colitis • Participants with diarrhea/colitis should be advised to drink liberal quantities of clear fluids. If sufficient oral fluid intake is not feasible, fluid and electrolytes should be substituted via IV infusion
AST or ALT elevation or Increased Bilirubin	Grade 2 ^a	Withhold	
 • Administer corticosteroids (initial dose of 0.5 - 1 mg/kg prednisone or equivalent) followed by taper 	
 • Monitor with liver function tests (consider weekly or more frequently until liver enzyme value returned to baseline or is stable)
	Grade 3 ^b or 4 ^c	Permanently discontinue	
 • Administer corticosteroids (initial dose of 1 - 2 mg/kg prednisone or equivalent) followed by taper 	
Type 1 diabetes mellitus (T1DM) or Hyperglycemia	New onset T1DM or Grade 3 or 4 hyperglycemia associated with evidence of β -cell failure	Withhold ^d	
 • Initiate insulin replacement therapy for participants with T1DM • Administer anti-hyperglycemic in participants with hyperglycemia 	
 • Monitor participants for hyperglycemia or other signs and symptoms of diabetes
Hypophysitis	Grade 2	Withhold	
 • Administer corticosteroids and initiate hormonal replacements as clinically indicated 	
 • Monitor for signs and symptoms of hypophysitis (including hypopituitarism and adrenal insufficiency)
	Grade 3 or 4	Withhold or permanently discontinue ^d		

Hyperthyroidism	Grade 2	Continue	
 Treat with non-selective beta-blockers (e.g., propranolol) or thionamides as appropriate 	
 Monitor for signs and symptoms of thyroid disorders
	Grade 3 or 4	Withhold or permanently discontinue ^d		
Hypothyroidism	Grade 2, 3, or 4	Continue	
 Initiate thyroid replacement hormones (e.g., levothyroxine or liothyronine) per standard of care 	
 Monitor for signs and symptoms of thyroid disorders
Nephritis: grading according to increased creatinine or acute kidney injury	Grade 2	Withhold	
 Administer corticosteroids (prednisone 1 – 2 mg/kg or equivalent) followed by taper 	
 Monitor changes of renal function
	Grade 3 or 4	Permanently discontinue		
Neurological Toxicities	Grade 2	Withhold	
 Based on severity of AE administer corticosteroids 	
 Ensure adequate evaluation to confirm etiology and/or exclude other causes
	Grade 3 or 4	Permanently discontinue		
Myocarditis	Grade 1	Withhold	
 Based on severity of AE administer corticosteroids 	
 Ensure adequate evaluation to confirm etiology and/or exclude other causes
	Grade 2, 3 or 4	Permanently discontinue		
Exfoliative Dermatologic Conditions	Suspected SJS, TEN, or DRESS	Withhold	
 Based on severity of AE administer corticosteroids 	
 Ensure adequate evaluation to confirm etiology and/or exclude other causes
	Suspected SJS, TEN, or DRESS	Permanently Discontinue		
Primary adrenal insufficiency	Grade 2	Withhold	
 Initiate hormonal replacement as clinically indicated. 	
 Monitor for signs and symptoms of adrenal insufficiency
	Grade 3 or 4	Withhold or permanently discontinue ^d		
All Other immune-related AEs (irAEs)	Intolerable/persistent Grade 2	Withhold	
 Based on severity of AE administer corticosteroids 	
 Ensure adequate evaluation to confirm etiology or exclude other causes
	Grade 3	Withhold or discontinue based on the event ^e		
	Grade 4 or recurrent Grade 3	Permanently discontinue		

^a AST/ALT: >3.0 – 5.0 x ULN if baseline normal; >3.0 - 5.0 x baseline, if baseline abnormal; bilirubin:>1.5 - 3.0 x ULN if baseline normal; >1.5 - 3.0 x baseline if baseline abnormal

^b AST/ALT: >5.0 to 20.0 x ULN, if baseline normal; >5.0 - 20.0 x baseline, if baseline abnormal; bilirubin:>3.0 - 10.0 x ULN if baseline normal; >3.0 - 10.0 x baseline if baseline abnormal

^c AST/ALT: >20.0 x ULN, if baseline normal; >20.0 x baseline, if baseline abnormal; bilirubin: >10.0 x ULN if baseline normal; >10.0 x baseline if baseline abnormal

^d The decision to withhold or permanently discontinue pembrolizumab is at the discretion of the investigator or treating physician. For participants with Grade 3 or 4 immune-related endocrinopathy where withhold of pembrolizumab is required,

pembrolizumab may be resumed when AE resolves to \leq Grade 2 and is controlled with hormonal replacement therapy or achieved metabolic control (in case of T1DM)

^e Events that require discontinuation include but are not limited to encephalitis and other clinically important irAEs (e.g., vasculitis and sclerosing cholangitis)

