Note: If after the evaluation of the event, it is determined not to be related to pembrolizumab, the Investigator does not need to follow the treatment guidance. Refer to Table 4-6 in Section 6 for guidelines regarding dose modification and supportive care.

It may be necessary to perform conditional procedures such as bronchoscopy, endoscopy, or skin photography as part of evaluation of the event.

Potential Drug Interactions:

No formal pharmacokinetic drug-drug interaction studies have been conducted with pembrolizumab or sacituzumab govitecan. SN-38 (the active metabolite of sacituzumab govitecan) is metabolized via human UDP-glucuronosyltransferase 1A1(UGT1A1). Concomitant administration of strong inhibitors or inducers of UGT1A1, with sacituzumab govitecan, should be avoided due to the potential to either increase (inhibitors) or decrease (inducers) the exposure to SN-38. If a patient requires a strong UGT1A1 inhibitor or inducer, they should not enroll onto this study or should stop study treatment if enrolled.

Strong UGT1A1 Inhibitors

Co-administration of sacituzumab govitecan with strong inhibitors of UGT1A1 (e.g., atazanavir, gemfibrozil, indinavir) may increase systemic exposure to the active metabolite, SN-38. Do not administer strong UGT1A1 inhibitors with sacituzumab govitecan unless there are no therapeutic alternatives.

Strong UGT1A1 Inducers

Exposure to SN-38 may be substantially reduced in patients concomitantly receiving UGT1A1 enzyme inducers (e.g., carbamazepine, phenytoin, phenobarbital, tipranavir, rifampicin, nelfinavir, ritonavir, efavirenz, lamotrigine, testosterone propionate). Do not administer strong UGT1A1 inducers with sacituzumab govitecan unless there are no therapeutic alternatives.

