held, and the other study drug may be administered (unless specified in the corresponding AE table of that study drug).

- For subjects on Arm A, if one study drug is delayed but the other study drug is given, then the study drug that was held should be re-initiated if appropriate at the next regularly scheduled administration time, i.e. if held on day 1 of the cycle, then sacituzumab govitecan could be restarted on day 8 of the cycle or day 1 of the next cycle (\pm 2 days for Day 1) and pembrolizumab could be restarted on day 1 of the next cycle (\pm 4 days).
- There must be a minimum of 14 days (\pm 2 days) between Day 8 and Day 1 of the next cycle of sacituzumab govitecan. There should be a minimum of 21 days \pm 4 days between administration of each dose of pembrolizumab.
- If treatment with sacituzumab govitecan is held or omitted due to an AE and the patient cannot be retreated with sacituzumab govitecan within 6 weeks from the last dose, sacituzumab govitecan should be permanently discontinued. Pembrolizumab can be continued per protocol (if the AE is considered unrelated to pembrolizumab).
- If treatment with pembrolizumab is held or omitted due to an AE and the patient cannot be retreated with pembrolizumab within 9 weeks from the last dose, pembrolizumab should be permanently discontinued. Sacituzumab govitecan can be continued per protocol (if the AE is considered unrelated to sacituzumab govitecan).
- For subjects on Arm A, if sacituzumab govitecan is discontinued and pembrolizumab is continued, Day 8 assessments (AE assessment, labs, vitals, etc.) are not needed.

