7.8 Routine Adverse Event Reporting

All Grade 2 or higher Adverse Events (excluding non-clinically significant laboratory values) Adverse Events **must** be reported in routine study data submissions to the Sponsor-Investigator on the toxicity case report forms. **AEs reported through expedited processes (e.g., reported to the IRB, FDA, etc.) must also be reported in routine study data submissions.**

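### Section 6.2 contradicts itself on Grade 1 myocarditis: the highlighted bullet bars any restart of pembrolizumab, while Table 4 only withholds the drug

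*Combined protocol and SAP*

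**What the plan says.** Section 6.2 treats withholding and permanently discontinuing pembrolizumab as two separate actions, chosen by severity, and says that the detailed rules are in Table 4. Between that statement and the table it highlights two steps:

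- "Permanently discontinue pembrolizumab for recurrent grade 2 pneumonitis"
- "Permanently discontinue pembrolizumab for any instance of myocarditis, regardless of grade"

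Table 4 then gives myocarditis two rows. The first is "Myocarditis Grade 1 Withhold". The second sets permanent discontinuation for Grades 2, 3 and 4.

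Section 6.1.1 governs what follows a hold. In Arm A, if one drug is given while the other is held, "the study drug that was held should be re-initiated if appropriate at the next regularly scheduled administration time". The outer limit is that, if the patient "cannot be retreated with pembrolizumab within 9 weeks from the last dose, pembrolizumab should be permanently discontinued". Section 6.2 adds that steroids given for a drug-related event must be down to 10 mg/day prednisone equivalent or less before pembrolizumab is restarted.

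Sites are pointed to these rules by two routes. Section 6.1.1 refers to the Section 6.2 guidance as a whole. Section 5.6.2 says "Refer to Table 4-6 in Section 6 for guidelines regarding dose modification and supportive care".

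**The concern.** One event, Grade 1 myocarditis attributed to pembrolizumab, receives two instructions that cannot both be followed once the patient has recovered. Under the bullet, the patient never receives pembrolizumab again. Under the table, the patient may be re-dosed. Two sites could handle the same case differently, and each could cite Section 6.2.

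What is at stake is patient safety and consistent conduct. A site working from the table could re-expose a patient to the drug after the one event for which the sponsor chose to highlight a stop at every grade.

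**Working it through.** There is no figure in the plan to reproduce, so the check is a comparison of texts.

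**Step 1. Set the two rules side by side, by grade.**

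| Myocarditis grade | Section 6.2 bullet | Table 4 row | Agree? |
|---|---|---|---|
| 1 | Permanently discontinue | Withhold | No |
| 2, 3 or 4 | Permanently discontinue | Permanently discontinue | Yes |

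**Step 2. Do the two actions differ in effect?** At onset they do not: the drug stops either way. Afterwards they do. A hold becomes permanent under Section 6.1.1 only if retreatment is not possible within 9 weeks of the last dose. With dosing every 3 weeks, the scheduled days in that window are weeks 3, 6 and 9. A patient held under the table can therefore miss the week 3 and week 6 doses and still be eligible for re-dosing at week 9. The bullet rules this out.

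**Step 3. Does anything reconcile them?**

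- *Precedence.* No statement was found that the bullets override the table, or the reverse. The other bullet, on recurrent Grade 2 pneumonitis, agrees with its Table 4 row, so it gives no example of a bullet departing from the table.
- *Discretion.* The rows that give the investigator latitude are marked with footnote d or e. The myocarditis rows carry neither.
- *Hold as a work-up step only.* The table separates Grade 1 from Grades 2 to 4. If every grade were to end in permanent discontinuation, the separate row would have no purpose.
- *Extraction fault.* This is unlikely here. The bullet is plain prose, and the table row is intact with its own grade and action. The general-instructions row of Table 4 has no visible content in the extracted text and should be checked in the PDF, but a general rule would be unlikely to reconcile two explicit myocarditis instructions.

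**Step 4. Size.** Action rows in Table 4: pneumonitis 2, diarrhea/colitis 2, liver tests 2, type 1 diabetes/hyperglycemia 1, hypophysitis 2, hyperthyroidism 2, hypothyroidism 1, nephritis 2, neurological 2, myocarditis 2, exfoliative skin conditions 2, adrenal insufficiency 2, other immune-related events 3.

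2 + 2 + 2 + 1 + 2 + 2 + 1 + 2 + 2 + 2 + 2 + 2 + 3 = 25.

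One of the 25 is in established conflict. Pembrolizumab is given only in Arm A, so only Arm A patients are affected, including any who are retreated with it.

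**The case against.** The best reply is that the practical gap is small, and much of it stands.

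- *A site is likely to see the strict rule.* Section 6.1.1 sends sites to Section 6.2 as a whole, where the bullet stands above Table 4 and is labelled a key step. This is right. But Section 5.6.2 sends sites to the tables, and a site that reads both is still not told which governs.
- *Withholding does not order a restart.* A reader might infer that the protocol directs re-dosing after Grade 1 myocarditis. It does not. Section 6.1.1 says only if appropriate, the 9 weeks are an outer limit, and Section 6.1 leaves continued treatment to the investigator in the absence of unacceptable toxicity. The defect is that the table leaves open what the bullet closes.
- *The event need not go unseen.* A reader might infer that, because routine reporting under Section 7.8 starts at Grade 2, a Grade 1 case would be invisible. That goes too far. Section 7.6 requires serious events in patients on pembrolizumab, including other important medical events, to reach the Sponsor-Investigator within 24 hours, and Section 7.8 brings expedited events into the routine data. Recording of concomitant therapy and steroid authorization (Section 5.6.1), and monitoring of drug administration (Appendix H, 4.1), may also show a case. Whether a Grade 1 case counts as serious is a matter of judgment. None of these routes settles the restart rule.
- *The stricter rule may not be the intended one.* If the bullets merely summarize the table, the bullet could be the error. The documents do not decide this, so the sponsor must confirm.

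A reader might also count the exfoliative skin rows as a second defect, because "Suspected SJS, TEN, or DRESS" appears as the trigger for both withholding and permanent discontinuation. Table cells extracted from a PDF can be misread, and nothing in Table 4 shows what the second trigger should be. It is an item to check and is not counted here.

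**Conclusion.** The point holds and should be fixed. For Grade 1 myocarditis, Section 6.2 gives two incompatible restart rules and no text was found to rank them. The conflict covers 1 of 25 action rows, one grade and one arm, and concerns only what happens after the drug has been stopped.

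It has no bearing on the primary endpoint, alpha, power or sample size. The documents give no rate for Grade 1 myocarditis and do not reproduce the CTCAE definition. Section 13.2.1 shows that accrual is complete, and the number of patients still receiving pembrolizumab is not stated. No probability or patient count can therefore be attached, and the documents do not support an inference that any patient was wrongly re-dosed. The allowance of 35 doses, with up to 17 further retreatment cycles, bounds how long the rule can apply. It does not measure an effect of the conflict.

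The conclusion assumes that the bullet and the Grade 1 row read in the source PDF as they do in the text, and that no rule ranking them stands in the general-instructions row of Table 4.

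**What to change.** In Table 4, change the Grade 1 myocarditis action from withhold to permanently discontinue, so that it matches the highlighted bullet. This is the stricter and safer alignment. The sponsor should confirm that it is the intended rule before the change is issued.

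In the same pass, check in the source PDF whether the two exfoliative skin rows really carry the same trigger. If they do, give them distinct triggers in the same amendment. Also check whether the general-instructions row of Table 4 has content.

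The cost is one table cell (two if the skin rows prove to be duplicated), a short amendment with IRB review (Appendix H, 3.7.1), implementation at external sites (Appendix H, 3.1) and one clarification letter. There is no statistical cost and no effect on patient numbers.

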6.2.1 Pembrolizumab Infusion-Related Reactions

Pembrolizumab may cause severe or life-threatening infusion-reactions including severe hypersensitivity or anaphylaxis. Signs and symptoms usually develop during or shortly after drug infusion and generally resolve completely within 24 hours of completion of infusion. Dose modification and toxicity management guidelines on pembrolizumab associated infusion reaction are provided in Table 5.

Table 5: Pembrolizumab Infusion Reaction Dose modification and Treatment Guidelines

NCI CTCAE Grade	Treatment	Premedication at Subsequent Dosing
Grade 1 Mild reaction; infusion interruption not indicated; intervention not indicated	Increase monitoring of vital signs as medically indicated until the participant is deemed medically stable in the opinion of the investigator.	None
Grade 2 Requires therapy or infusion interruption but responds promptly to symptomatic treatment (e.g., antihistamines, NSAIDs, narcotics, IV fluids); prophylactic medications indicated for ≤24 hrs	
Stop Infusion.
 
Additional appropriate medical therapy may include but is not limited to:
 
IV fluids Antihistamines NSAIDs Acetaminophen Narcotics
 
Increase monitoring of vital signs as medically indicated until the participant is deemed medically stable in the opinion of the investigator. If symptoms resolve within 1 hour of stopping drug infusion, the infusion may be restarted at 50% of the original infusion rate (e.g., from 100 mL/hr to 50 mL/hr). Otherwise, dosing will be held until symptoms resolve and the participant should be premedicated for the next scheduled dose.
 
Participants who develop Grade 2 toxicity despite adequate premedication should be permanently discontinued from further study drug treatment
	Participant may be premedicated 1.5h (± 30 minutes) prior to infusion of pembrolizumab with: Diphenhydramine 50 mg po (or equivalent dose of antihistamine). Acetaminophen 500-1000 mg po (or equivalent dose of analgesic).
Grades 3 or 4 Grade 3: Prolonged (i.e., not rapidly responsive to symptomatic medication and/or brief interruption of infusion); recurrence of symptoms following initial improvement; hospitalization indicated for other clinical sequelae (e.g., renal impairment, pulmonary infiltrates) Grade 4: Life-threatening; pressor or ventilatory support indicated	
Stop Infusion.
 
Additional appropriate medical therapy may include but is not limited to:
 
Epinephrine** IV fluids Antihistamines NSAIDs Acetaminophen Narcotics Oxygen Pressors Corticosteroids
 
Increase monitoring of vital signs as medically indicated until the participant is deemed medically stable in the opinion of the investigator. Hospitalization may be indicated.
 
**In cases of anaphylaxis, epinephrine should be used immediately.
 
Participant is permanently discontinued from further study drug treatment.
	No subsequent dosing
Appropriate resuscitation equipment should be available at the bedside and a physician readily available during the period of drug administration. For further information, please refer to the Common Terminology Criteria for Adverse Events v4.0 (CTCAE) at http://ctep.cancer.gov		

6.2.2 Non-Immune Related Toxicities associated with Pembrolizumab

Non-irAEs will be managed as appropriate, following clinical practice recommendations. For any intolerable or persistent Grade 2 toxicities and Grade 3 toxicities (excluding endocrinopathy) lasting 12 weeks or longer after the last dose of pembrolizumab, pembrolizumab should be permanently discontinued.

6.3 Management of Toxicities Attributable to Sacituzumab Govitecan

NCI-CTCAE v5.0 is used to grade the severity of all AEs. The guidelines for management of toxicities associated with sacituzumab govitecan are based on the assessment of severity according to these criteria. Toxicities should be managed in accordance with standard medical practice and treatment guidelines. All clinically appropriate imaging or laboratory testing should be utilized to fully assess a toxicity to determine the appropriate treatment. Appropriate follow-up studies should be utilized to follow all toxicities to resolution. Patients with known UGT1A1 *28 polymorphism may have a higher risk of developing treatment related toxicities. Additional monitoring may be required in those patients.

Dose Delays – Sacituzumab Govitecan

Sacituzumab govitecan is to be administered in 21-day cycles on Day 1 and Day 8; the next cycle should start 14 days (\pm 2 days) after the Day 8 dose (i.e., the Day 8 infusion will be counted as the first day of that 14-day period). Visit windows of \pm 2 days from the scheduled infusion are permitted. The scheduled Day 1 and Day 8 infusions may be delayed for treatment-related toxicities. For Day 8 dosing, if the toxicity has not resolved to \leq Grade 2 within 1 week, Day 8 dosing of that cycle should be omitted and dosing should resume with the Day 1 of the following cycle. There should be a minimum of 7 days (\pm 2 days) between the Day 1 and the Day 8 infusions. There should be a minimum of 14 days (\pm 2 days) between the Day 8 infusion and the Day 1 infusion of the next cycle.

For patients randomized to the combination arm, if drugs are administered on different days in the same 21-day cycle, every effort should be made to administer both drugs on the same day in subsequent cycles (all assessments being adjusted accordingly), provided that criteria are met per protocol and that 14 days (\pm 2 days) have elapsed since the administration of the previous dose of sacituzumab govitecan and 21 \pm 4 days since the administration of the previous dose of pembrolizumab. If Day 8 sacituzumab govitecan dosing is delayed, causing adjustment to Day 1 of the following cycle, it is recommended to administer pembrolizumab on the same day as Day 1 of the next cycle of sacituzumab govitecan.

Dose Reductions and Discontinuation

The major toxicities of sacituzumab govitecan are expected to be gastrointestinal symptoms and hematologic suppression. All subjects will be closely monitored over the course of their treatment and aggressively medically managed, including dose reduction and interruption, in order to prevent the need for treatment discontinuation and serious complications of these toxicities. Sacituzumab dose reductions and interruptions will be managed based on toxicity severity, as assessed by NCI CTCAE v5.0. The sacituzumab govitecan dose must not be re-escalated following a dose reduction. The table below summarizes recommendations for sacituzumab govitecan dose reductions and discontinuations for treatment-related toxicities.

Dose holds for anemia are not mandated but can be applied as clinically indicated. Supportive care (i.e., red blood cell transfusions) may be managed according to institutional guidelines.

Table 6: Recommended Dose Reduction Schedule for Sacituzumab Govitecan

Event NCI CTCAE v5.0	Occurrence	Recommended dose reduction or action
Severe Neutropenia		
Grade 4 neutropenia \geq 7 days OR Grade 3-4 febrile neutropenia, OR At time of scheduled treatment, Grade 3-4 neutropenia which delays dosing by 2 or 3 weeks for recovery to \leq Grade 1	First	25% dose reduction and administer granulocyte-colony stimulating factor (G-CSF)*
	Second	50% dose reduction and administer G-CSF*
	Third	Discontinue treatment and administer G-CSF*
At time of scheduled treatment, Grade 3-4 neutropenia which delays dosing beyond 3 weeks for recovery to \leq Grade 1	First	Discontinue treatment and administer G-CSF*
Severe Non-Neutropenic Toxicity		
Grade 4 non-hematologic toxicity of any duration, OR Any \geq Grade 3 nausea, vomiting or diarrhea due to treatment that is not controlled with antiemetics and anti-diarrheal agents**, OR Other \geq Grade 3 non-hematologic toxicity persisting >48 hours despite optimal medical management, OR At time of scheduled treatment, \geq Grade 3 non-neutropenic hematologic or non-hematologic toxicity, which delays dose by 2 or 3 weeks for recovery to \leq Grade 1	First	25% dose reduction
	Second	50% dose reduction
	Third	Discontinue treatment
\geq Grade 3 non-neutropenic hematologic or non-hematologic toxicity, which does not recover to \leq Grade 1 within 3 weeks	First	Discontinue treatment

*Prophylactic administration of growth factors may be considered if clinically indicated (See Section 6.3.3)

**Sacituzumab govitecan may be dose reduced for recurring Grade 2 diarrhea that is not controlled with antidiarrheal agents.

